2.1.4.2 Hypoglycemia

Hypoglycemia endpoints are described in Section 2.1.3.2.1.

2.1.4.3 Deaths

The death observation period are per the observation periods defined above.

- Death on-study: deaths occurring during the on-study observation period
- Death pre-treatment: deaths occurring before the on-study observation period
- Death on-treatment: deaths occurring during the treatment-emergent adverse event period
- Death post-study: deaths occurring after the end of the study

2.1.4.4 Laboratory safety variables

Clinical laboratory data consist of blood analysis, including hematology, clinical chemistry, and urinalysis. Clinical laboratory values after conversion will be analyzed into standard international units and international units will be used in all listings and tables.

For purposes of determining patient eligibility, blood sampling for central laboratory assessments and urine sample collection will be performed at visit 1.

- Hematology: blood count (erythrocytes, hemoglobin, hematocrit, leukocytes, platelets);
- Clinical chemistry: total bilirubin (in case of values above the normal range, differentiation in conjugated and non-conjugated bilirubin), AST, ALT, alkaline phosphatase (ALP), creatinine, estimated GFR, sodium, potassium;
- C-Peptide at Visit 1 only for those patients that a documented C-Peptide value is not available in the source document.
- Urine analysis (assayed by the central laboratory): pH, glucose, ketones, leucocytes, blood/hemoglobin, protein;
- Serum pregnancy test in women of childbearing potential (WOCBP) at screening and urine pregnancy test at most onsite visits will be performed. Urine pregnancy tests can be performed more often if needed and confirmed by a serum test if positive.

Note: Any abnormal laboratory value estimated as clinically significant by the investigator should be immediately rechecked (whenever possible using the central laboratory) for confirmation before making a decision of permanent discontinuation of IMP for the concerned patient. Any confirmed laboratory abnormality estimated as clinically significant by the investigator must be reported as an AE/SAE as applicable.

Technical formulas are described in [Section 2.5.1](#).

2.1.4.5 Vital signs variables

Vital signs include: sitting blood pressure, and pulse measurements which will be recorded with the patient in a sitting position for 5 minutes before the measurement is taken.

2.1.4.6 Electrocardiogram variables

Not applicable.

2.1.5 Pharmacokinetic variables

Not applicable.

2.1.6 Pharmacodynamic/genomics endpoints

Not applicable.

2.1.7 Quality-of-life endpoints

Not applicable.

2.1.8 Health economic endpoints

Not applicable.

2.2 DISPOSITION OF PATIENTS

This section describes patient disposition for both patient study status and the patient analysis populations.

Screened patients are defined as any patient who met the inclusion criteria and signed the informed consent.

Randomized patients consist of all patients who have been allocated a treatment kit number as recorded in the IVRS/IWRS database, regardless of whether the treatment kit was used or not.

Patients treated without being randomized will not be considered as randomized and will not be included in any efficacy population.

For any patient randomized more than once, only the data associated with the first randomization will be used in any analysis population. The safety experience associated with any later randomization will be assessed separately.

For patient study status, the total number of patients in each of the following categories will be presented in the clinical study report using a flowchart diagram or summary table:

- Screened patients
- Screen failure patients and reasons for screen failure
- Nonrandomized but treated patients
- Randomized patients
- Randomized but not treated patients
- Randomized and treated patients
- Patients who did not complete the study treatment period as per protocol
- Patients who discontinued study treatment by main reason for permanent treatment discontinuation
- Status at last study contact

For all categories of patients (except for the screened and nonrandomized categories) percentages will be calculated using the number of randomized patients as the denominator. Reasons for treatment discontinuation will be supplied in tables giving numbers and percentages by treatment group.

All critical or major deviations potentially impacting efficacy analyses, randomization, and drug-dispensing irregularities, and other major or critical deviations will be summarized in tables giving numbers and percentages of deviations by treatment group.

Additionally, the analysis populations for safety, efficacy will be summarized in a table by number of patients on the randomized population.

- Efficacy population: modified Intent-to-Treat (mITT) population, which will consist of all patients who are randomized and who have a post-baseline CGM assessment and enough data to calculate the primary endpoint, percent of time in range.
- Safety population

Treatment Persistence

- Kaplan–Meir plots (estimate) of cumulative incidence of permanent IMP discontinuation will be provided by treatment arm on the safety population.
- The hazard ratio of IMP permanent discontinuation of Toujeo arm over Lantus will be estimated along with its 95% CI on the safety population using a Cox regression model.

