1 OVERVIEW AND INVESTIGATIONAL PLAN

1.1 STUDY DESIGN AND RANDOMIZATION

This is a multicenter, randomized, active-controlled, parallel group, 16-week open-label study. The study consists of an up to 4-week screening and Continuous Glucose Monitoring (CGM) training period and a 16-week treatment period (simple titration versus carbohydrate counting).

Patients satisfying the inclusion/exclusion criteria and CGM requirements are randomized 1:1 to morning injection of either Toujeo or Lantus. The randomization is stratified by baseline HbA1c (<8%, ≥8%), frequency of Lantus insulin injections at screening BID vs QD, current CGM use (yes/no) and mealtime insulin titration algorithm.

Approximately 616 patients are randomized, aiming for approximately 524 patients with evaluable data.

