2.3.2 Safety population

The safety population will be comprised of all patients who take at least one dose of randomized treatment, and will be analyzed as-treated (according to the treatment actually received). In addition:

- Randomized patients for whom it is unclear whether they took the study medication will be considered as treated and included in the safety population.
- For patients receiving more than one study treatment during the trial, the treatment group allocation for as-treated analysis will be the treatment group in which he/she is treated for longer.

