2.4.4.2 Analyses of secondary efficacy endpoints

The main secondary efficacy endpoints.

The seven main secondary efficacy endpoints will be analyzed as below and tested sequentially after the primary endpoint. Testing strategy is described in 2.4.4.3

The incidence (proportion of patients with any nocturnal symptomatic hypoglycemia events) will be analyzed using logistic regression, adjusting for randomization strata and other baseline characteristics (duration of diabetes, baseline BMI and age) if the model permits.

The risk ratio (RR) of hypoglycemia of Toujeo versus Lantus will be assessed by a log-binomial regression model adjusting for randomization strata and other baseline characteristics (duration of diabetes, baseline BMI and age) if the model permits.

The rate (number of events per patient-year) of nocturnal symptomatic hypoglycemic events will be analyzed using an over-dispersed Poisson regression model, adjusting for randomization strata and other baseline characteristics (duration of diabetes, baseline BMI and age) if the model permits.

The mean change of each participant's glucose level during the last four hours of CGM data collection prior to next day basal insulin injection comparing Toujeo versus Lantus will be analyzed using a mixed model, in which treatment arm is a fixed categorical effect and patient is a random effect, adjusting for randomization strata and other baseline characteristics (duration of diabetes, baseline BMI and age) if the model permits. If a patient has more than 7 evaluable days of CGM data, only the first 7 days closest to Week 15 will be included.

The percentage of time glucose concentrations obtained by CGM within the target range of 70-140 mg/dL (3.9-7.8 mmol/L) during the last 4 hours of CGM data prior to the next day basal insulin injection will be summarized and analyzed by the same model as the primary endpoint.

Total, within day and between day standard deviation (SD) will also be summarized and analyzed by the same model as the primary efficacy endpoint.

Other endpoints

The total, within day and between day CV% and SD will be summarized at baseline and study endpoint by treatment group using mean, median, standard deviation, minimum and maximum, and will be analyzed as for the primary endpoint.

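### The treatment-persistence comparison groups patients as-treated, so the group label can depend on the outcome; group by randomized arm and name the Cox covariates

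*SAP*

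**What the plan says.** The persistence analysis appears at the end of SAP section 2.2; Protocol section 11.2 has no counterpart. It has two parts, and both use the safety population. The plot is of "cumulative incidence of permanent IMP discontinuation will be provided by treatment arm on the safety population". The hazard ratio, Toujeo arm over Lantus, is "estimated along with its 95% CI on the safety population using a Cox regression model". No covariates or strata are named.

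SAP section 2.3.2 limits the safety population to patients with at least one dose, grouped by the treatment they received. For patients with more than one study treatment, "the treatment group allocation for as-treated analysis will be the treatment group in which he/she is treated for longer". Uncertain cases stay in: "Randomized patients for whom it is unclear whether they took the study medication will be considered as treated and included in the safety population".

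The disposition tables in the same section 2.2 work differently. They use randomized patients as the denominator and give "Randomized but not treated patients" a line of their own. SAP section 2.2.1 adds separate listings of patients randomized but not treated and of patients who did not follow their randomized arm.

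On stratification, SAP section 1.1 states: "The randomization is stratified by baseline HbA1c", followed by basal injection frequency, current CGM use and mealtime titration algorithm. The hypoglycemia models in SAP section 2.4.4.2 are specified as "adjusting for randomization strata and other baseline characteristics (duration of diabetes, baseline BMI and age) if the model permits".

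**The concern.** As-treated grouping is conventional for adverse events, where the question is which drug the patient was exposed to. Here the question is whether patients stay on the product they were assigned. For a patient who received both products, the label is fixed only after follow-up, by comparing time on each. Time on product is also the outcome, so the label is not independent of the event.

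The wording does not settle the matter either. Section 2.2 speaks of the Toujeo arm, which reads as the randomized arm, while the population it names is regrouped by treatment received. The disposition table, on randomized patients, and the persistence curve, on regrouped dosed patients, could show different counts for the same outcome in the same section.

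Separately, the Cox model is the only between-arm model planned for discontinuation, and its covariates are left open. What is at stake is how clearly a descriptive result can be interpreted; no confirmatory claim depends on it.

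**Working it through.** **1. Is there a figure to reproduce?** The SAP gives no event count, hazard ratio or power for persistence. Its nearest figures are 308 randomized per arm and 15% dropout (SAP section 1.3): 308 × 0.85 = 261.8, matching the stated 262. They serve below only as a scale. The 15% is a dropout assumption, not a stated discontinuation rate.

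**2. Can the label depend on the event if only kit errors count?** Yes. The flow chart has dispensing at randomization and Weeks 4, 8 and 12. Take a hypothetical patient randomized to Toujeo, correctly supplied to Week 4 and given Lantus kits in error from then on.
- Stops at Week 7: 4 weeks on Toujeo, 7 − 4 = 3 on Lantus. Counted as Toujeo, with an event.
- Continues to Week 16: 4 weeks on Toujeo, 16 − 4 = 12 on Lantus. Counted as Lantus, without an event.

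The same patient with the same dispensing error changes group according to whether and when treatment stops.

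**3. Are the randomization factors named elsewhere?** The primary model (SAP section 2.4.4.1) names them, as do the logistic, log-binomial and Poisson hypoglycemia models, the mixed model for the last four hours, and the MMRM for HbA1c and FPG (all section 2.4.4.2). The persistence model in section 2.2 names none.

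**4. How large could the shift be?** The documents give no discontinuation, switching or non-starter rate, so all of these are assumptions: 308 per arm, proportion d discontinuing in each arm, true hazard ratio 1.
- Events = 616 × d. Factor either side of the hazard ratio for its 95% interval = exp(1.96 × 2/√events). At 15%: events = 92.4, factor = exp(1.96 × 0.208) = 1.50.
- Moving k discontinuers from arm A to arm B: pA = (308d − k)/(308 − k), pB = (308d + k)/(308 + k), hazard ratio B/A = ln(1 − pB)/ln(1 − pA). At 15%, k = 1: pA = 45.2/307 = 0.1472, pB = 47.2/309 = 0.1528, ratio 1.04.
- Counting a net excess of k non-starters in one arm as events: hazard ratio = ln(1 − (308d + k)/308)/ln(1 − d). At 15%, k = 1: (46.2 + 1)/308 = 0.1532, ratio 1.02.

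| d | Events | 95% factor | Discontinuers moved, k = 1 / 3 / 6 | Excess non-starters counted, k = 1 / 3 / 6 |
|---|---|---|---|---|
| 5% | 30.8 | 2.03 | 1.14 / 1.47 / 2.23 | 1.07 / 1.20 / 1.40 |
| 10% | 61.6 | 1.65 | 1.06 / 1.20 / 1.45 | 1.03 / 1.10 / 1.21 |
| 15% | 92.4 | 1.50 | 1.04 / 1.13 / 1.27 | 1.02 / 1.07 / 1.14 |

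Moves in the other direction give the reciprocals. The moved-patient column is a worst case: every moved patient discontinues and all move the same way. Only one of the 18 values (2.23) exceeds the sampling factor for its row. These are systematic shifts, however, and a confidence interval does not cover them.

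**The case against.** The case against has real force, and most of it limits the size of the point.

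- **Switching after stopping.** A reader might infer that anyone who stops Toujeo and then takes marketed Lantus for longer is moved to the Lantus group. The documents do not support that. The rule concerns study treatments. Kits are allocated centrally (Protocol section 8.5). After permanent discontinuation patients return to standard of care (Protocol section 10.4.4), and later basal insulin is the treating physician's choice (Protocol section 8.10). On the natural reading mainly dispensing errors remain, and these are monitored and listed.
- **Non-starters.** Protocol section 10.4.2 defines permanent discontinuation as a decision not to re-expose the patient, which presupposes exposure. Dosed patients are therefore a defensible risk set. The first injection is to be supervised on the randomization day, with a next-morning exception (Protocol section 8.2.4), so known non-starters should be few. Patients with unclear dosing are kept, so it would be wrong to say that all possible non-starters are dropped.
- **Covariates.** Calling the Cox model unadjusted goes beyond the text, which is silent. Omitting the strata would not by itself make the comparison non-randomized, and the as-treated rule changes a patient's arm, never the stratum.
- **Link to the primary analysis.** A reader might infer that discontinuation is the main route to the 15% loss, or that this hazard ratio will be used to judge differential loss. No passage says either. Patients are followed after stopping IMP. Evaluability also depends on having enough CGM days and on prohibited medication (SAP section 2.4.4.1).
- **Status.** Persistence is not among the tests ordered in SAP section 2.4.4.3.

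What survives is narrower: the label can depend on the outcome even with kit errors alone, the arm wording conflicts with the as-treated population, and the covariates are unstated.

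**Conclusion.** The point holds as a small, low-cost improvement to a descriptive analysis. As planned, the persistence hazard ratio is not strictly a comparison of randomized arms, because patients given both products are placed by time on drug, and its covariates are unspecified.

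The practical effect is probably small. At 15% discontinuation, one to three moved discontinuers would shift the ratio by 4% to 13%, and one to three excess non-starters by 2% to 7%. At 5% the shifts are 14% to 47% and 7% to 20%. All of these rest on assumed counts and rates, and the moved-patient figures are worst cases. With few or no kit errors, the as-treated and as-randomized results would nearly coincide. The primary result and the testing hierarchy are unaffected.

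**What to change.** Amend the Treatment Persistence text in SAP section 2.2 as follows.

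1. Group the Kaplan-Meier curves and the Cox model by randomized arm.
2. Include the four randomization factors in the Cox model, if the model permits, in line with the SAP's other models.
3. Add a sensitivity run on all randomized patients, with time measured from randomization and known non-starters counted as events on Day 1. SAP section 2.5.1 defines Day 1 as the first IMP administration, so this run needs its own statement that Day 1 is the day of randomization. It also widens the event beyond the Protocol's definition of discontinuation, which is why it belongs as a sensitivity analysis.
4. Keep the as-treated safety-population version as supporting.

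The cost is SAP wording before database lock and a few extra runs. All the data are already collected.

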2.2.1 Randomization and drug dispensing irregularities

Randomization and drug-dispensing irregularities occur whenever:

1. A randomization is not in accordance with the protocol-defined randomization method, such as a) an ineligible patient is randomized, b) a patient is randomized based on an incorrect stratum, c) a patient is randomized twice, or d) in a dynamic randomization scheme the treatment assignment is, in fact, not random, due to a computer program error.

OR

2. A patient is dispensed an IMP kit not allocated by the protocol-defined randomization, such as a) a patient at any time in the study is dispensed a different treatment kit than as randomized (which may or may not contain the correct-as-randomized IMP), or b) a nonrandomized patient is treated with IMP reserved for randomized patients.

Randomization and drug-dispensing irregularities will be monitored throughout the study and reviewed on an ongoing basis.

All randomization and drug-dispensing irregularities will be documented in the clinical study report. If the number of irregularities is large enough to make a tabular summary useful, the irregularities will be categorized and summarized among randomized patients (number and percentages).

Patients with the following deviations will be identified and described in separate listings:

- Treated but not randomized
- Randomized but not treated
- Randomized but not following the treatment arm as randomized

Randomization and drug-dispensing irregularities to be prospectively identified include but are not limited to:

Randomization and drug allocation irregularities
Kit dispensation without IVRS transaction
Erroneous kit dispensation
Kit not available
Randomization by error
Patient randomized twice
Forced randomization
Stratification error
Patient switched to another site

2.3 ANALYSIS POPULATIONS

Patients treated without being randomized will not be considered randomized and will not be included in any efficacy population.

The randomized population includes any patient who has been allocated to a randomized treatment regardless of whether the treatment kit was used.

For any patient randomized more than once, only the data associated with the first randomization will be used in any analysis population. The safety experience associated with any later randomization will be assessed separately.

The safety experience of patients treated and not randomized will be reported separately, and these patients will not be in the safety population.

2.3.1 Efficacy populations

2.3.1.1 Modified Intent-to-treat/Modified intent-to-treat population (mITT)

The efficacy analysis population will be the mITT population, which will consist of all patients who are randomized and who have a post-baseline CGM assessment and enough data to calculate the primary endpoint, percent of time in range of 70-180mg/dL (3.9–10mmol/L) during Week 16. Patients will be analyzed as-randomized.

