11.3.1 Efficacy populations

11.3.1.1 Modified intent-to-treat population

The efficacy analysis population will be the modified Intent-to-Treat (mITT) population, which will consist of all patients who are randomized and who have at least one post-baseline assessment of the endpoint of interest.

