2.1.3.2.1 Hypoglycemia

2.1.3.2.1.1 Hypoglycemia classification

Hypoglycemia observation periods

- **Pre-treatment hypoglycemia events** are events that occur during the pre-treatment period
- **Treatment-emergent hypoglycemia events** are events that occur during the on-treatment period
- **Post-treatment hypoglycemia events** are events that occur during the post-treatment period

Hypoglycemia events will be categorized as defined in [Appendix A](#). The glucose values used to classify hypoglycemia events are from the hypoglycemia e-CRF rather than the glucose values from CGM or central laboratory.

The incidence (proportion of patients with any hypoglycemia events) and the rate (number of events per patient year of exposure) will be assessed during each safety observation period for each hypoglycemia category.

In case of some classification items are missing (i.e. assistance required or not, presence of symptom, glycemic values, use of countermeasure) to determine hypoglycemia classification (see Section 2.5.3) the following categories will be presented.

- Not classified – non severe
- Not classified – severity unknown

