2.4.4.3 Multiplicity issues

Results of the secondary analyses are considered as informative only if the primary analysis is positive, and will be examined in a hierarchical step-down manner. The primary efficacy endpoint, the percentage of time glucose in target range 70-180mg/dL (3.9–10 mmol/l) during Week 16, will be tested first, followed by (1) incidence of nocturnal symptomatic hypoglycemia, (2) rate of nocturnal symptomatic hypoglycemia, (3) mean change of each participant's glucose level during the last four hours of CGM (4) percentage (%) of time glucose concentrations obtained by CGM within target range of 70-140 mg/dL (3.9–7.8 mmol/L) during the last 4 hours of CGM data collection prior to next day basal insulin injection, (5) total CV%, (6) within day CV% and (7) between day CV% . Each test was planned to be performed at 5% significance level. Inferential conclusions about these successive efficacy endpoints will require statistical significance of the previous one.

For other secondary and exploratory endpoints, nominal p-values will be presented for information only.

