2.4.5.3 Analyses of hypoglycemia variables

Hypoglycemia analyses described in Section 2.4.4.2 will be repeated based on Safety Population.

The incidence and rate (nocturnal or 24 hours) of all hypoglycemic events will be analyzed for the hypoglycemia categories of severe, documented symptomatic, asymptomatic, probable and relative, as defined in the publication of the ADA Workgroup on Hypoglycemia, 2015.

The incidence (proportion of patients with any nocturnal symptomatic hypoglycemia events) will be analyzed using logistic regression, adjusting for randomization strata and other baseline characteristics (duration of diabetes, baseline BMI and age) if the model permits.

The risk ratio (RR) of hypoglycemia of Toujeo versus Lantus will be assessed by a log-binomial regression model adjusting for randomization strata and other baseline characteristics (duration of diabetes, baseline BMI and age) if the model permits.

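### The SAP's single CGM-evaluable efficacy population, an unlisted change from the protocol, by inference also governs the two confirmatory nocturnal hypoglycemia tests, which do not need CGM data

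*SAP*

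**What the plan says.** - **Protocol 11.3.1.1** (and the synopsis) makes the mITT specific to each endpoint: "all patients who are randomized and who have at least one post-baseline assessment of the endpoint of interest".
- **SAP 2.3.1.1** makes the mITT the efficacy analysis population and restricts it to "all patients who are randomized and who have a post-baseline CGM assessment and enough data to calculate the primary endpoint", analyzed as randomized. SAP 2.2 repeats this: "Efficacy population: modified Intent-to-Treat (mITT) population, which will consist of all patients who are randomized and who have a post-baseline CGM assessment". No other efficacy population is defined.
- **SAP 2.1.3.2** lists incidence and rate of nocturnal symptomatic hypoglycemia among the main secondary efficacy endpoints. SAP 2.4.4.2 says "The seven main secondary efficacy endpoints will be analyzed as below and tested sequentially after the primary endpoint" and names no population for them. SAP 2.4.4.3 puts them directly after the primary endpoint: "1) incidence of nocturnal symptomatic hypoglycemia, (2) rate of nocturnal symptomatic hypoglycemia".
- **SAP 2.4.5.3**: "Hypoglycemia analyses described in Section 2.4.4.2 will be repeated based on Safety Population". SAP 2.3.2 defines that population as "all patients who take at least one dose of randomized treatment, and will be analyzed as-treated (according to the treatment actually received").
- **SAP 2.1.3.2.1**: "The glucose values used to classify hypoglycemia events are from the hypoglycemia e-CRF rather than the glucose values from CGM or central laboratory".
- **SAP 1.5 and 1.6** list added CGM parameters and clarifications, pooling of the two CGM weeks, one added endpoint and a rule for events within 30 minutes of each other. The population change is not among them. Protocol section 11 does allow an SAP to revise the protocol's statistical section.

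**The concern.** Sufficient end-of-study CGM is a natural entry condition for time in range. It is not one for nocturnal hypoglycemia, which is taken from the hypoglycemia e-CRF and recorded throughout the study. Applying it there decides who enters two confirmatory tests by events after randomization: early withdrawal, failed CGM or use of prohibited medication. In an open-label trial those events may be related to the assigned treatment, so the two tests lose part of the protection that randomization gives. A reader comparing the protocol with SAP 1.5 and 1.6 would not learn that the population had changed.

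**Working it through.** **1. Which population governs the two tests?** No sentence states it, so it has to be inferred.
- Both are efficacy endpoints (SAP 2.1.3.2).
- The SAP has one efficacy population, and it needs evaluable CGM (SAP 2.3.1.1).
- The analysis section gives no exception (SAP 2.4.4.2).
- The safety-population analysis is described as a repeat (SAP 2.4.5.3), which implies that the confirmatory run is on something else.

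Hierarchy steps (1) and (2) therefore fall on the CGM-evaluable mITT.

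**2. Who is left out?**
- Patients who withdraw before Week 15 (SAP 2.1.3, item 8). That item excludes them only from the primary analysis; SAP 2.3.1.1 extends the exclusion to every efficacy endpoint.
- Patients without 4 usable days even after the repeat week and pooling (SAP 2.1.3, item 7).
- Patients who received prohibited medication (SAP 2.4.4.1).

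The last two groups can complete all 16 weeks. Patients who stop study insulin are also followed to the scheduled end of the study (protocol 10.4.4). Omitted patients may thus contribute anything from little to full follow-up.

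**3. The plan's own figures.** Inputs from SAP 1.3: difference 4, SD 14, two-sided 5%, 90% power, 262 evaluable and 308 randomized per arm, 15% dropout.
- n per arm = 2 × (1.960 + 1.282)² × 14² / 4² = 258 (259 with the t distribution).
- Power at 262 = Φ(4 / (14 × √(2/262)) − 1.960) = Φ(1.310) = 90.5% (90.4% with t).
- 262 / 0.85 = 308.2, and 308 × 0.85 = 261.8.

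The primary sample size reproduces. The 80% hypoglycemia power cannot be reproduced, because no control rate or overdispersion is given; below it is taken as exactly 80% with 262 per arm.

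**4. Share of patients.** 616 − 524 = 92; 92/616 = 46/308 = 14.9%.

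**5. Share of follow-up and power.** Let f be the mean fraction of the 16 weeks that an omitted patient contributes (assumption, 0.25 to 1), with equal omission in both arms and full follow-up in the 262. Sixteen weeks = 112/365.25 = 0.3066 years.
- Share left out = 46f / (262 + 46f).
- Power with these patients added back, for the same rate ratio and information proportional to follow-up = Φ(2.802 × √((262 + 46f)/262) − 1.960), where 2.802 = 1.960 + 0.842.

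| f | Share left out | Patient-years, both arms | Power if added back |
|---|---|---|---|
| 0.25 | 11.5/273.5 = 4.2% | 7.1 of 167.7 | 81.7% |
| 0.5 | 23/285 = 8.1% | 14.1 of 174.8 | 83.2% |
| 1 | 46/308 = 14.9% | 28.2 of 188.9 | 85.9% |

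**6. Which period?** SAP 2.1.3 runs all efficacy on both an on-treatment and a randomized period. SAP 2.1.3.1 names the randomized period for the primary endpoint. SAP 1.3 and protocol 11.1 describe the hypoglycemia rate endpoint as covering events at any time after randomization, which points to the randomized period. SAP 2.1.3.2.1 instead assesses incidence and rate by safety observation period. No analysis section settles the matter for steps (1) and (2).

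**The case against.** **The safety repeat covers the gap.** This is the strongest reply and much of it stands. SAP 2.4.5.3 pre-specifies the same analyses on all treated patients, so the omitted patients' events are reported. That set would differ from an as-randomized analysis mainly for patients who received the other treatment or whose dosing is unclear. It is still as-treated and is not the basis of the hierarchy, so it cannot stand in for the confirmatory tests.

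**No planned power is lost.** Correct. SAP 1.3 already bases the hypoglycemia power on 262 evaluable patients per arm. The gain in the table is a by-product; the point is selection.

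**The 15% is only a dropout allowance.** Also correct. It is a planning assumption and not the share that the rule must omit. The actual share may be smaller or larger.

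**Stronger readings that the documents do not support.**
- A reader might infer that the population could be picked once the data are seen. The same text that creates the problem fixes the population, by inference, as the CGM-evaluable mITT, so that charge fails.
- A reader might infer that the period is wholly open. The sample-size wording points to the randomized period for the rate test; what is missing is confirmation in an analysis section, and any equivalent statement for the incidence test.
- A reader might infer that the hypoglycemia results are biased toward Toujeo. Nothing in the documents gives a direction or a size.

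**Conclusion.** The point holds and should be fixed. The SAP replaces an endpoint-specific population with a CGM-evaluable one without listing the change, and the first two confirmatory secondary tests inherit it although their endpoint does not need CGM. The population for these tests is an inference from four SAP sections; if it is rejected, they have no stated population and the same edit is needed.

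Under the planning assumption, up to about 15% of randomized patients are omitted. The omitted follow-up is 4.2% to 14.9%, and restoring it would lift an exact 80% power to about 82% to 86%. These figures rest on the assumed f, equal omission by arm and an unchanged rate ratio. Bias may be zero. The primary test is not affected.

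**What to change.** 1. In SAP 2.3.1.1 and 2.2, apply the CGM-data requirement to CGM endpoints only. For hierarchy steps (1) and (2), restore the endpoint-specific mITT of protocol 11.3.1.1, analyzed as randomized.
2. In SAP 2.4.4.2, name that population and the randomized period as confirmatory for both steps, in line with SAP 1.3 and 2.1.3.1. Keep the on-treatment period as sensitivity.
3. List the change in SAP 1.6.
4. Keep the CGM-evaluable and safety-population analyses as supportive.

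Cost: wording in four SAP sections and no new data, since hypoglycemia events and dosing dates are already in the e-CRF. One small downside is that early leavers bring unequal follow-up into the incidence test.
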